### **13.0 CRITERIA FOR REMOVAL FROM STUDY**

If at any time the patient develops progressive disease or experiences an unacceptable toxicity, the patient will be referred to receive standard treatment. An unacceptable toxicity is defined as severe frequency, dysuria or pain. Patients that cannot tolerate BCG instillations and refuse due to side effects are also defined as unacceptable toxicity. These patients will be evaluable for the primary endpoint of the study.

Patients with progressive disease will be considered to have experienced treatment failure, and patients with toxicities will have their outcomes ascertained 6 months after the initiation of the first BCG treatment. The number of patients, who do not complete therapy, and the reasons for not completing therapy, will be included in the final study report.

If at any time the patient is found to be ineligible for the protocol as designated in the section on Criteria for Patient/Subject Eligibility (i.e., a change in diagnosis), the patient will be removed from the study.

Patients who are removed from the study due to withdrawal of consent or who are lost to follow-up will not be considered evaluable and will be replaced.

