### **3.6 Rationale**

1. The standard care for patients with high-risk non-muscle-invasive bladder cancer who do not respond to BCG treatment is radical cystectomy. Surgery with radical cystectomy is associated with a complication rate of up to 60%, as well as with poor self-image owing to external urine collecting devices. There is a need for a more efficient non-surgical approach for patients with these tumors.
2. The current treatment regimen of 6 intravesical treatments with BCG is arbitrary. The proposed study will test the efficacy of a new regimen of BCG treatments.

3. The proposed study will attempt to define the acceptable clinical toxicity profile of intravesical BCG.
4. There is a need to increase the durability of the response to intravesical BCG; the treatment regimen in the proposed study will attempt to address this.
5. The proposed study will incorporate recent data that provided new insight into the T cell activity in response to BCG therapy. Furthermore, we will focus on the idea that priming the immune system will result in a more robust immunologic response against any tumor that is present.

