### 4.3 Intervention

**Rationale:** The current regimen of 6 intravesical instillations of BCG for high risk superficial bladder cancer is arbitrary. No randomized trials have been performed to identify the optimal number of intravesical BCG instillations needed to obtain the lowest recurrence rates.

**Treatment Plan:** Patients with high risk superficial bladder cancer will be treated with 2 induction courses (12 intravesical instillations total) of BCG. Patients will undergo a diagnostic TUR which will include a urine cytology when possible to evaluate their bladder tumor/tumors, a past TURBT and urine cytology within 60 days of treatment initiation will also suffice. If the pathological characteristics of the tumors result in the patient being deemed eligible, they will be asked to enroll in the study. A prior/current history and physical examination will also be evaluated. After the first induction course (6 intravesical instillations) of BCG, patients will be scheduled for a cystoscopy at 3 months (+/- 4 weeks). During this 3 month cystoscopy appointment patients will again submit a urine cytology prior to the procedure. If worsening tumor is found a TURBT will be scheduled at the physicians discretion. All enrolled patients will be evaluated for the primary endpoint, as defined in section 14.0, of the study, regardless of whether they received the full course of treatment.

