## 12.0 CRITERIA FOR THERAPEUTIC RESPONSE/OUTCOME ASSESSMENT

Patient response/outcome will be assessed by both urine cytology and cystoscopy at 6 months after initiation of therapy.

Patients who have a response are those who have no evidence of disease in their bladder by both urine cytology and cystoscopy.

Patients whose disease remains at the same stage or is downstaged without complete resolution are considered nonresponders and will be documented as having recurred. Any positive result for either cystoscopy or cytology exam will be followed by TURBT at the physician's discretion.

Patients with worsening tumor, defined as the upstaging from non-muscle invasive to muscle invasive disease, or metastatic disease will be documented as disease progression.

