#### **Primary endpoint**

The study will employ a single-stage design. We are interested in the 2-induction BCG therapy if the overall response rate is  $\geq 80\%$  after the initiation of the first BCG therapy and not interested if the overall response rate is  $\leq 66\%$ . The probabilities of a type I error and type II error are set at 0.05 and 0.20, respectively. We will continue enrolling patients until 75 patients have completed their second cystoscopy on study. On completion of the trial, if  $\geq 52$  patients had a response, the regimen will be declared effective and of interest. All patients who meet the eligibility criteria for the study and enroll in it will be included in the analysis, regardless of whether they completed the full 2 BCG induction courses.

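### Could responses that follow another bladder cancer therapy, after BCG is stopped for toxicity, distort the primary response count without the report showing it?

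*Combined protocol and SAP*

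**What the plan says.** Section 13.0 provides that a patient who "experiences an unacceptable toxicity, the patient will be referred to receive standard treatment". These patients stay evaluable for the primary endpoint, and "patients with toxicities will have their outcomes ascertained 6 months after the initiation of the first BCG treatment". Progressive disease is handled differently in the same section: it is set to treatment failure.

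Two other sections agree on who is counted. Section 4.3 evaluates all enrolled patients "regardless of whether they received the full course of treatment". Section 14.0 (Primary endpoint) includes all eligible enrolled patients "regardless of whether they completed the full 2 BCG induction courses".

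Section 12.0 defines response by examination alone: "Patients who have a response are those who have no evidence of disease in their bladder by both urine cytology and cystoscopy".

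On reporting, section 13.0 commits the final report to the number of patients who do not complete therapy, and "the reasons for not completing therapy, will be included in the final study report". Section 14.0 adds only a 6-month progression rate with a confidence interval. Section 16.1 says that source documentation will support the computerized record but lists no individual data items.

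**The concern.** The trial asks what two induction courses of BCG achieve. It answers with one responder count judged against a fixed 66%, with no control arm. The plan sends toxicity stops to other care and then counts whatever the bladder shows at 6 months. If that care includes another bladder cancer therapy, a clearance due to that therapy would count for BCG.

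Nothing else in the documents closes this off:

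- Standard treatment is not defined after a toxicity stop. Section 3.6 names a standard only for patients "who do not respond to BCG treatment is radical cystectomy". After cystectomy a section 12.0 response could not be shown by cystoscopy, so the worry is confined to bladder-sparing therapy.
- The section 6.3 bars on radiation, chemotherapy and surgery are entry criteria.
- The removal clause in section 13.0 ("If at any time the patient is found to be ineligible for the protocol") gives a change in diagnosis as its example. It does not clearly reach therapy started after a toxicity stop.
- Numbers and reasons for stopping do not show what was given afterwards.

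At stake would be a declaration of effectiveness that rests partly on another treatment.

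**Working it through.** **1. The plan's own rule.** Inputs from section 14.0: n = 75, success at 52 or more responses, rates 0.66 and 0.80, type I error 0.05, type II error 0.20. Exact binomial: P(X ≥ 52 | 75, 0.66) = 0.317 and P(X ≥ 52 | 75, 0.80) = 0.990. The stated error rates are not reproduced. That is a separate and larger matter, and it does not depend on how toxicity stops are handled.

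**2. What the planned report can show.** Let R be the counted responders, T the patients who stopped for toxicity, and X the counted responses among them that followed another therapy. The report gives T, provided reasons are tabulated as counts. Since 0 ≤ X ≤ T, responses not following other therapy number R − X ≥ R − T.

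- If R − T ≥ 52, a positive decision cannot depend on later therapy.
- If R + T < 52, a negative decision cannot depend on it either.

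At the target rate the expected R is 75 × 0.80 = 60. The margin over 52 is then 60 − 52 = 8 toxicity stops. With a cutoff of 57 (not in the plan; the smallest with exact type I error at or below 0.05) the margin would be 60 − 57 = 3. The bound is useful but may not settle a close result.

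**3. Size and direction.** The documents give no switching rate, so s = 3%, 5% and 10% of 75 patients are assumed. Change in expected responders when BCG alone would give 66%:

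| Assumption about switchers | Formula | 3% | 5% | 10% |
|---|---|---|---|---|
| Two thirds of would-be nonresponses convert | 75 × s × 0.34 × 2/3 | +0.51 | +0.85 | +1.70 |
| Clear at 66% | 75 × s × 0 | 0 | 0 | 0 |
| Clear at 50% | −75 × s × 0.16 | −0.36 | −0.60 | −1.20 |

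The first row implies that switchers clear at 0.66 + 0.34 × 2/3 = 0.887. That exceeds the 80% hoped for from the full regimen, and it would apply to patients who could not tolerate BCG. Section 3.3 points the other way: it reports better recurrence-free rates for resection with BCG than for resection with intravesical chemotherapy, and says newer approaches, intravesical chemotherapies among them, have not succeeded. Those are other populations, so the direction stays open. Error rates built on these assumed inputs would suggest more precision than the documents support.

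**4. What a supplementary count would add.** Suppose patients with other therapy were scored as nonresponders and the true rate were 80%, also among switchers. The count would discard 75 × s × 0.80 = 1.8, 3.0 or 6.0 true responses on average. Its chance of reaching 52 would fall from 0.990 to 0.964, 0.928 or 0.743. It would also not isolate BCG-only clearance, because sections 4.3 and 10.0 allow a discretionary resection at 3 months.

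**5. Comparability with the benchmark.** The 66% matches 100% − 34% from the institutional audit in section 3.3. The documents do not say how that audit treated patients who changed therapy. If it used observed outcomes, the primary rule is like-for-like and the supplementary count would be the mismatched one.

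**The case for a change.** The best case for a change is that it is cheap and harmless. One dated data item and one extra count would leave the primary analysis and decision rule alone, and would tell the reader directly whether the headline count includes responses after other therapy. The cap T is only a cap: it does not identify the patients and may be too wide in a close result. Nor can toxicity stops be assumed negligible. Section 13.0 counts refusal because of side effects as unacceptable toxicity, and section 11.1 expects irritative symptoms in about 60% of patients, although that is not a stopping rate.

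Much of this stands. The term is undefined for these patients, and the planned report would not name the responders concerned. But a switch to another anticancer therapy is inferred rather than stated. Section 1.0 describes the present standard as one BCG induction course, which a patient stopping in the second course has already had. Section 11.1 describes symptomatic treatment for complaints that overlap with those defining unacceptable toxicity. What remains is a wish for added reporting, and it shows no rule to be wrong or biased.

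**Conclusion.** No change to the plan is needed. Using the observed 6-month status of toxicity stops is a pre-specified and defensible choice, and the three sections that govern it agree. The remaining gap is descriptive. The planned report bounds the number of counted responses that could have followed another therapy but does not identify them. An analyst preparing the final report could state that number where source records hold it, without touching the primary analysis or the decision rule.

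On assumed switching of 3% to 10%, the average shift runs from about 1.2 responders fewer to 1.7 more among 75, with zero in between. The upper end needs a clearance rate among switchers of about 89%, which nothing in the documents supports. These figures rest on assumed switching and clearance rates, and the bound rests on reasons for stopping being reported as counts. Documented evidence that many patients receive another bladder-sparing therapy before the 6-month assessment would give the point more weight.

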## 4.1 OVERVIEW OF STUDY DESIGN/INTERVENTION

### 4.2 Design

[figure not shown]
The study will use a single-stage phase II design. We are interested in the 2-induction BCG therapy if the overall response rate is  $\geq 80\%$  and not interested if the overall response rate is  $\leq 66\%$ . The probabilities of a type I error and type II error are set at 0.05 and 0.20, respectively.

We will enroll/continue enrolling patients until 75 patients have completed their second cystoscopy on study. On completion of the trial, if  $\geq 52$  patients had a response, the regimen will be declared effective and of interest.

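### The responder count that decides the trial has no fixed denominator: 75 is implied, but the analysis-set, replacement and accrual rules do not settle on it

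*Combined protocol and SAP*

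**What the plan says.** Three rules bear on who is counted.

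- **Analysis set.** Section 14.0 (Primary endpoint): "All patients who meet the eligibility criteria for the study and enroll in it will be included in the analysis", whether or not both induction courses were completed. Section 4.3 agrees: "All enrolled patients will be evaluated for the primary endpoint", whatever treatment was received.
- **Removal and replacement.** Section 13.0 says of patients removed for these reasons: "withdrawal of consent or who are lost to follow-up will not be considered evaluable and will be replaced". It treats two other groups differently: "If at any time the patient develops progressive disease or experiences an unacceptable toxicity, the patient will be referred to receive standard treatment", and "These patients will be evaluable for the primary endpoint of the study". Progressors count as treatment failures. Patients who stop for toxicity have their outcome ascertained at 6 months.
- **Accrual stop and decision.** Section 14.0: "We will continue enrolling patients until 75 patients have completed their second cystoscopy on study"; section 4.2 says the same. If at least 52 "patients had a response, the regimen will be declared effective and of interest". Neither section prints a denominator next to the 52.

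The accrual estimate in section 14.0 is 3-5 patients per month. Section 10.0 places the second cystoscopy at 6 months, plus or minus 4 weeks.

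**The concern.** Taken together, the rules leave three candidate denominators: all eligible enrolled patients, evaluable patients (without withdrawals and losses), and patients with a second cystoscopy. The 75 belongs to the third set and is written as a stopping rule for accrual, not as the N of the analysis.

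The success rule is a fixed number of responders, so its false-positive rate depends on how many patients could contribute to it. If the set is larger than the cutoff was calculated for, an uninteresting regimen passes too easily. If the set is limited to patients who reached the second cystoscopy, the observed rate is too high whenever those who did not reach it respond less often. In a single-arm trial with one decision threshold, an unfixed denominator also leaves room to settle it after outcomes are known.

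**Working it through.** **Inputs.** Uninteresting rate 0.66, target rate 0.80, type I error 0.05 and type II error 0.20 (sections 4.2 and 14.0); 75 second cystoscopies and at least 52 responders (same sections); 3-5 patients per month (section 14.0, Accrual); assessment at 6 months plus or minus 4 weeks (section 10.0). The documents give no rate of loss, and no number of progressors who miss the second cystoscopy, so both are assumed below.

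**Formula.** Type I error of a rule r of N is P(X >= r), with X binomial(N, 0.66). Power uses 0.80. The test is taken as one-sided because the rule is an upper-tail count; the documents do not state sidedness.

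**1. The plan's own figure.** 52 of 75 gives type I error 0.317 and power 0.990, so the stated 0.05 and 0.20 are not reproduced. The smallest cutoff that holds 0.05 at N=75 is 57 (error 0.041, power 0.844). A cutoff of 52 is the exact one for N=68 (error 0.042, power 0.812). This is a separate fault. The steps below use cutoffs that are right for their N, so that it is not counted twice.

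**2. Assessed patients added to the set, cutoff unchanged.**

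| Cutoff | N | Type I error |
|---|---|---|
| 57 | 75 | 0.041 |
| 57 | 76 | 0.060 |
| 57 | 79 | 0.150 |
| 57 | 93 | 0.857 |
| 57 | 105 | 0.995 |
| 52 | 68 | 0.042 |
| 52 | 69 | 0.062 |
| 52 | 72 | 0.161 |

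The N=93 and N=105 rows are 75+18 and 75+30. If accrual is not paused, the patients on study but not yet assessed at the 75th second cystoscopy number about 6 x 3 = 18 to 6 x 5 = 30. With the extra 4 weeks, taken as a seventh month, the range is 7 x 3 = 21 to 7 x 5 = 35. Those two rows apply only if every such patient is counted against an unchanged cutoff. The last three rows show that the sensitivity is the same whichever of 52 and 75 is corrected.

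**3. Progressors outside the 75.** Suppose k progressors have no second cystoscopy and are certain failures, and the true rate over all 75+k patients is 0.66. The rate among the 75 is then 0.66 x (75+k)/75.

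- k=1: 0.669; P(X >= 57 of 75) = 0.057
- k=2: 0.678; 0.078
- k=4: 0.695; 0.136

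**4. Withdrawals and losses.** Scored as nonresponders on top of the 75, they add nothing to the responder count. The decision is unchanged and only the reported rate falls. If they are excluded, a share d with response rate r leaves a rate of (0.66 - d x r)/(1 - d) among those assessed. At 57 of 75 with r = 0.50 (assumed):

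- d=0.05: (0.66 - 0.025)/0.95 = 0.668; error 0.056
- d=0.10: (0.66 - 0.05)/0.90 = 0.678; error 0.078

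In the extreme case that none of them respond, the errors are 0.134 and 0.354.

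**5. Cutoffs tied to N.** Smallest r with type I error at most 0.05 (error; power): 57/75 (0.041; 0.844), 60/79 (0.0375; 0.851), 63/83 (0.034; 0.857), 70/93 (0.035; 0.896), 78/105 (0.043; 0.940).

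**The case against.** The best defence is that the passages deal with different things. The inclusive sentences in sections 4.3 and 14.0 both end with a clause about incomplete treatment, while section 13.0 deals with missing outcomes and is the more specific rule. Read that way, the plan has a recognisable evaluable set: toxicity stoppers are assessed at 6 months, progressors are failures, and withdrawals and losses are replaced. This largely stands. A reader might infer a flat contradiction between sections 13.0 and 14.0, and the documents do not support that; what is missing there is a stated exception. The defence still does not fix N, because nothing requires a progressor to have the second cystoscopy that accrual counts, and nothing says what becomes of patients enrolled beyond the 75th.

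Three stronger readings are tempting.

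- *Any extra patient inflates the error.* Not so. Withdrawn or lost patients scored as nonresponders leave the count alone. The rise in step 2 needs patients who can respond.
- *The error will reach 0.857 or more.* The documents do not say that accrual runs on unpaused or that overrun patients count towards the threshold. Section 14.0's wording allows that reading without establishing it.
- *This explains the 0.317.* It does not. That error is present with N fixed at exactly 75.

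It is also fair to object that 57/75 and 52/68 are reconstructions, not the trial's printed rule, and that the numbers of progressors and losses are assumed. Both are true, and they are why the point is conditional.

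**Conclusion.** The concern holds as a should-fix point. The denominator is implied to be 75 but is not fixed, and the type I error of a fixed count depends on it. Once the cutoff is right for 75, a few evaluable failures outside the 75 move the error from 0.041 to between 0.057 and 0.136 (one to four progressors, assumed). Excluding 5% or 10% who respond at 50% (assumed) moves it to 0.056 or 0.078. Counting overrun patients against an unchanged cutoff would do far more, but only if accrual is not paused and they are counted.

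The mismatch between 52 and 75 is the larger fault. Repairing it would not repair this one, because the plan would still not say of how many patients the new count is taken. A reader might infer from the N=68 match that 75 is the wrong number; the documents do not show which of the two is wrong.

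**What to change.** 1. **One primary set, worded alike in sections 4.2, 4.3, 13.0 and 14.0.** Do not define it by having a second cystoscopy. A workable form is the first N evaluable eligible patients in enrolment order, whatever treatment they completed. Progression before the 6-month assessment counts as a failure within N, with or without a second cystoscopy. If replacement of withdrawals and losses is kept, the replacement is the next eligible patient in order. Stop accrual when that N is reached. State in advance whether overrun patients are reported separately or included with the cutoff recalculated.
2. **State the rule as r of N.** Let r be the smallest count with exact type I error at most 0.05 at the actual N, as in step 5. The sponsor must first reconcile 52 with 75.
3. **One sensitivity analysis.** Report the response rate in all eligible enrolled patients with every missing 6-month outcome counted as nonresponse, beside the evaluable-only rate.

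The cost is wording in four sections and one extra analysis, with no added patients or visits. The downside of item 3 is that it is conservative. At a true 80% with 5% missing at random (assumed), the rate is 0.80 x 0.95 = 0.76 and the chance of reaching 60/79 is about 0.57. With 10% missing it is 0.80 x 0.90 = 0.72, and the chance of reaching 63/83 is about 0.25. It should therefore inform the reading of the result and not decide the trial.

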### **14.0 BIOSTATISTICS**

A detailed explanation of the study design including the rational for the research can be found in section 3.0 of the protocol.

#### **Primary endpoint**

The study will employ a single-stage design. We are interested in the 2-induction BCG therapy if the overall response rate is  $\geq 80\%$  after the initiation of the first BCG therapy and not interested if the overall response rate is  $\leq 66\%$ . The probabilities of a type I error and type II error are set at 0.05 and 0.20, respectively. We will continue enrolling patients until 75 patients have completed their second cystoscopy on study. On completion of the trial, if  $\geq 52$  patients had a response, the regimen will be declared effective and of interest. All patients who meet the eligibility criteria for the study and enroll in it will be included in the analysis, regardless of whether they completed the full 2 BCG induction courses.

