## **9.1 TREATMENT/INTERVENTION PLAN**

Patients enrolled in the study will receive 6 consecutive intravesical BCG treatments. After the 3 month follow-up cystoscopy appointment, patients will undergo another set of 6 intravesical BCG treatments. Each set of BCG treatments will include 6 injections within a recommended 6 weeks, a regimen that is within the standard of care. Any delay of treatment will be allowable per standard of care BCG treatment procedures. Such disruptions may include but are not limited to unforeseen circumstances, institutional holidays, or patients's schedule.

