## **10.0 EVALUATION DURING TREATMENT/INTERVENTION**

3 months (+/- 4 weeks) after initiation of therapy

- Urine cytology
- Cystoscopy
- TUR will be scheduled (at physician's discretion)

6 months (+/- 4 weeks) after initiation of therapy

- Urine cytology
- Cystoscopy
- TUR will be scheduled (at physician's discretion)

Evaluation	Pretreatment screening	3 months (+/- 4 weeks) after initiation of therapy	6 months (+/- 4 weeks) after initiation of therapy
History and physical	x		

Urine cytology	X	X	X
Cystoscopy		X	X
Trans-urethral resection tumor*	X (within 60 days of treatment initiation)	X (*will be scheduled at physician's discretion)	X (*will be scheduled at physician's discretion)

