## **Accrual**

We estimate 3-5 patients per month will be accrued to this protocol.

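### Closing enrolment on 75 completed 6-month cystoscopies enrols about 18-30 patients beyond 75, and all who are eligible count toward a fixed cutoff of 52 responders

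*Combined protocol and SAP*

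**What the plan says.** Section 14.0 (Primary endpoint) sets the enrolment rule: "We will continue enrolling patients until 75 patients have completed their second cystoscopy on study". Section 4.2 repeats it: "We will enroll/continue enrolling patients until 75 patients have completed their second cystoscopy on study". Section 10.0 schedules on-study cystoscopies at "3 months (+/- 4 weeks) after initiation of therapy" and "6 months (+/- 4 weeks) after initiation of therapy". Its table marks none at pretreatment, so the second on-study cystoscopy is the 6-month one.

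On accrual, Section 14.0 says: "We estimate 3-5 patients per month will be accrued to this protocol". Section 13.0 provides for replacement only of patients who withdraw consent or are "lost to follow-up will not be considered evaluable and will be replaced". Patients later found ineligible are removed, with no mention of replacement.

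Section 14.0 sets the uninteresting and interesting response rates at 66% and 80%. It adds: "The probabilities of a type I error and type II error are set at 0.05 and 0.20, respectively". Success is 52 or more responders, with no denominator attached to that number. The same paragraph puts all eligible enrolled patients into the analysis, whether or not they finished both courses. The available text gives no ceiling on total enrolment, no pause in accrual, and no rule for patients who are enrolled but not yet assessed when the 75th patient completes.

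**The concern.** A single-stage design needs a known number of patients. Here the number enrolled depends on how fast the site recruits, because accrual runs on through the whole follow-up lag whether or not anyone needs replacing. Two things are at stake.

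- **Exposure.** Patients enter the two-course regimen after enough have been enrolled to make the planned decision.
- **The decision rule.** The extra patients enter the analysis, but the number of responders needed for success does not move. Each additional patient makes 52 responders easier to reach, so faster accrual alone makes a positive conclusion more likely.

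**Working it through.** **1. The plan's own figures.** The documents state no expected total enrolment, so there is none to reproduce. The stated decision rule can be checked with the exact binomial:

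- P(X >= 52 | n = 75, p = 0.66) = 0.317, against the stated type I error of 0.05.
- P(X >= 52 | n = 75, p = 0.80) = 0.990, against the implied power of 0.80.

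The rule does not reproduce. That is a separate conflict between 75 and 52, and it is the baseline for step 4.

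**2. Size of the overrun.** Inputs are accrual of 3-5 per month (Section 14.0, Accrual) and a lag of 6 months from start of therapy to second cystoscopy (Section 10.0). Overrun = accrual rate x lag.

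- 3 x 6 = 18, so 75 + 18 = 93 enrolled (18/75 = 24% over).
- 5 x 6 = 30, so 75 + 30 = 105 enrolled (30/75 = 40% over).

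Four weeks is about 0.92 months, so the edges of the visit window are about 5.08 and 6.92 months. These give 3 x 5.08 = 15.2 to 5 x 6.92 = 34.6. Those extremes require every patient to sit at the same edge of the window. In a simulation with Poisson accrual and visits spread uniformly over the window, the mean overrun was 18.0, 24.1 and 30.1 at 3, 4 and 5 per month (90% ranges 11-25, 16-32 and 21-40).

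Two assumed quantities, neither given in the documents, raise the count:

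- A lag of 0.5-1 month from enrolment to first instillation gives means of about 19-35.
- If a fraction d never has the second cystoscopy, enrolment beyond 75 is 75/(1 - d) + 6 x rate - 75. For d = 10% this is 26-38. Only 75/0.9 - 75, about 8, of these are true replacements; the other 18-30 are structural.

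**3. How many are still being treated.** Section 9.1 says: "After the 3 month follow-up cystoscopy appointment, patients will undergo another set of 6 intravesical BCG treatments". It recommends 6 weeks per course, so instillations end at about 3 + 1.5 = 4.5 months. Under steady accrual, 4.5/6 = three quarters of the extra patients, about 14-22, are within the treatment phase when the target is met. Most of the rest have finished instillations and await the 6-month visit.

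**4. Effect on the decision.** Exact binomial, with the cutoff fixed at 52 and all enrolled patients counted:

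| Patients analysed | Expected responders at 66% | 52 as a share | Chance of >= 52 at 66% | Smallest cutoff with type I error <= 0.05 | Its type I error | Its power at 80% |
|---|---|---|---|---|---|---|
| 75 | 49.5 | 69.3% | 0.317 | 57 | 0.041 | 0.844 |
| 93 | 61.4 | 55.9% | 0.983 | 70 | 0.035 | 0.896 |
| 105 | 69.3 | 49.5% | 0.9998 | 78 | 0.043 | 0.940 |

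At 93 or 105 patients, 52 lies well below the number of responders expected from a regimen of no interest.

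**The case against.** The strongest reply is that counting completers is a recognisable trade-off: it avoids a late restart of accrual and accepts more patients. The extra patients also narrow the confidence interval for the progression rate. This stands as a reason someone might choose the rule. However, the protocol gives no such reason, no expected total and no adjustment of the cutoff. The rule may have been meant only to cover replacements, but neither section says so.

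Three stronger readings are tempting and are not supported:

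- **That all 18-30 extra patients would be under treatment, with 12 unneeded instillations each.** About a quarter would be past the treatment phase. Section 1.0 calls one 6-instillation course the current standard of care, so the study-specific addition is the second course.
- **That the overrun is what breaks the type I error.** It is already 0.317 at 75 patients. The overrun takes it from there to near certainty.
- **That the trial had no enrolment ceiling.** Some pages are not in the public copy, and a ceiling may stand there. What can be said is that the available text has none and that the operative sentence contradicts one.

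It might also be said that only the first 75 completers would be counted. That would hold the figure at 0.317, but it conflicts with the instruction in Section 14.0 to analyse all eligible enrolled patients.

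**Conclusion.** The point holds. Followed as written, the rule enrols about 18-30 patients beyond 75, for a total of about 93-105, before any dropout. Because the analysis takes in all eligible enrolled patients against an unchanged cutoff, the chance of a false success at a 66% response rate rises from 0.317 to between 0.983 and 0.9998.

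This rests on steady accrual at the stated 3-5 per month, a 6-month lag, no ceiling elsewhere, and the extra patients being eligible, followed to 6 months and counted. The enrolment figure does not depend on the separate 75/52 conflict; the error rates do, since they take 52 as given.

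**What to change.** In Sections 4.2 and 14.0, replace the enrolment sentence with a rule that:

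1. pauses accrual once the planned number of evaluable patients is enrolled (75, or whatever number is set when the 75/52 conflict is resolved);
2. reopens one slot for each patient who withdraws, is lost to follow-up, or is found ineligible and removed;
3. states that the cutoff applies to that fixed denominator or, failing that, is recomputed for the actual evaluable number as the smallest count with exact type I error of at most 0.05 at 66% (for example 57 of 75, 70 of 93, 78 of 105).

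Section 13.0 should be brought into line on replacing ineligible patients. If a total-accrual ceiling exists on a page not available here, reconcile it with these sentences.

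**Cost.** This is a wording change. With no losses it adds no time: the 75th patient enters at 75/3 = 25 or 75/5 = 15 months and is assessed 6 months later under either rule. With losses, each late replacement delays study end by its recruitment time plus about 6-7 months. At an assumed 10% loss, the 18-30 patients still in follow-up at the pause would yield about 2-3 late replacements. The chance that at least one of those is also lost is 1 - 0.9^2 = 19% to 1 - 0.9^3 = 27%, which would extend the delay again.
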